5.9. Sample Size and Power. The power calculations are based on our previous study and other published studies. We found an AHI reduction from 32.2 ± 5.6 SD to 24.6 ± 4.4 (7.6 or 24%) following a 12-week exercise protocol, and the attrition rate was 11%.¹⁹ The standard deviation of the change in AHI was large (13), perhaps because of the relatively short intervention duration and small sample size compared with what are proposed. In a recent meta analysis of the effect of dietary weight loss on AHI, we find an average reduction of AHI of 34% in studies involving weight loss of approximately 10% over intervention durations of 12-20 weeks.¹⁸ Based on this finding, we assume a reduction of total AHI from 32.2 ± 5.6 to 21.25 ± 5.2 following the Weight Loss Alone treatment (10.9 or ~34% reduction). A previous study indicated a 46% reduction in total AHI (from 21.7 ± 9.0 to 11.8 ± 6.8) following exercise and weight loss.²⁷ Based on these data, in calculating power, we assume decreases in AHI of increasing magnitude will be observed following exercise alone, weight loss alone, and exercise + weight loss. We assume a reduction of AHI from 32.2 ± 5.6 to 17.3 ± 5.2 (14.9 or 46% reduction) after exercise + weight loss, and we assume 10% attrition. In our power calculations, the overall significance level is set at $\alpha = 0.05$. To insure we will have sufficient testing power, order-restricted tests are not considered in power estimation, but this type of testing will be applied in our data analyses to test the hypothesized pattern.

To ensure power for the **Primary Hypothesis (Compared with exercise alone and weight loss alone, exercise+weight loss will elicit significantly greater improvements in AHI)** we consider weight loss alone vs. exercise+weight loss. We set the significance level at 0.025 to adjust for multiple testing. With $n=30$

per treatment, the power is 86% to detect an average difference of 4 (14.9 vs 10.9, or 46% vs 34%) in AHI reduction between the treatments assuming treatment standard deviations of 5. The power is 82.2% with a 10% attrition. We expect higher statistical power to compare exercise alone vs. exercise+weight loss.

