For **Secondary Hypothesis 1, Compared with exercise alone and weight loss alone, exercise + weight loss will elicit significantly greater improvements in OSA at 3-month follow-up**, we anticipate decreases in compliance, resulting in greater within-treatment variability and/or lower between-treatment differences, and less powerful between-treatment tests. As such, we consider 82% to be an upper bound power estimate of this hypothesis. If, for example, at follow-up, the magnitude of the effect of condition were only 80% of that anticipated at post-test, power to detect significant differences would be approximately 65%.

For **Secondary Hypothesis 2, Compared with baseline, each treatment will elicit significant improvements in AHI**, the power calculation is based on paired one-sided t-tests to test the reduction of AHI. Since there are 3 treatments, multiple-testing Bonferroni-adjusted significance level is set at $0.05/3=0.017$. For exercise alone, from our preliminary data, we set the mean±SD reduction in AHI (baseline minus post-treatment) at 7.6 ± 12.5 (24% reduction) for the power calculation. The standard deviation is smaller than in our preliminary study because of the longer duration and larger sample size. With $n=30$, tests should have power of 86.0% to detect such a post-exercise difference. With 10% attrition, our tests should have power of 82% to detect this change. Also, we propose a 16 wk treatment, which is a longer than in our previous study and may result in larger reduction with smaller variance. We expect that the AHI reduction will be at least as great as seen in our previous study. Because we expect that weight loss alone and exercise+weight loss will elicit larger effects than exercise alone, the power to detect changes in AHI will be greater for these other treatments.

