For **Secondary Hypothesis 3, Compared with exercise alone and weight loss alone, exercise + weight loss will elicit significantly greater improvements in measures of co-morbidity**, we use PSQI, systolic blood pressure, and hemoglobin a1c for power calculations. Power is estimated based on two-sample t-tests on the changes (post-treatment minus baseline) of each variable. Having repeated measures for some of these variables will further increase power. Similar treatment effects are assumed for weight loss alone and exercise alone. In this hypothesis, since the outcomes of interests were chosen based on previous studies instead of random selection, alpha for each test is set at 0.05. For Hypothesis 3, $n=30$ per treatment will result in power of ~80% on all the tests except for SBP with minimum detectable differences determined based on our preliminary data (**Table 3**). The power is close to 80% for PSQI and hemoglobin a1c, but 42-47% for systolic blood pressure, assuming 10% attrition. There is clearly sufficient power to detect baseline-to-post improvements for the co-morbidity variables following each individual treatment. Here we focus on effects of weight loss only and exercise only. At alpha of .05, for PSQI, the detectable average reduction is set at 1.5 with standard deviation of 1.8 (for both treatments). Estimated power is 99% with 30 subjects in each group and assuming 10% attrition. For SBP, power is 96% to detect a reduction of 6.7 with standard deviation of 10 with 30 subjects in the group and 10% attrition. Finally, for Ha1c, power is >.99 to detect an average reduction of 0.2% with standard deviation 0.1% assuming 10% attrition. In summary, with 30 subjects in each of the three treatment groups, we are confident that our tests will have power of 80% for most outcome variables.

Table 3. Statistical power under different reduction scenarios for Secondary Hypothesis 3.

PSQI *Reduction=1.5 SD _{diff} =1.8		SBP Reduction=6.7 SD _{diff} =10		Ha1c Reduction=0.2 (%) SD _{diff} =0.1 (%)	
#Diff	Power	Diff	Power	Diff (%)	Power
1.15	78.8%	3.8	42.5%	0.07	85.0%
1.26	85.0%	4.12	47.3%	0.077	90.4%

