5.10. Statistical Analysis. We will first examine univariate and bivariate statistics to determine the distributional characteristics of study variables and to identify potentially relevant background covariates and confounders. For the **Primary Hypothesis and Secondary Hypotheses 1 and 3**, we will use an analysis of covariance (ANCOVA) approach to examine treatment effects on post-intervention (i.e., immediate post-test for Primary Hypothesis and Secondary Hypothesis 3; 3-month follow-up for Secondary Hypothesis 1) outcome values (i.e., AHI scores for Primary Hypothesis and Secondary Hypothesis 1; comorbidity measures for Secondary Hypothesis 3), with treatment as the primary independent variable, and adjusting for baseline outcome value, intervention dose (percentage of sessions attended), baseline outcome value, age, sex,

duration of OSA diagnosis, plus any other relevant covariates. We will test for ordering of treatment means (not adjusted for covariates) via order-restricted tests within the R package flexisoreg. Next, we will test for overall differences among treatment groups on post-treatment AHI values with order-restricted comparisons (isotonic contrasts) of covariate-adjusted means to test for the predicted ordered patterning of the three treatment means. For **Secondary Hypothesis 2**, we will examine the effect of time point (pre- vs. post-treatment) on AHI scores at each treatment level (i.e., test “simple main effects” of time) in the context of a repeated measures ANCOVA. Analyses will be based on an intent-to-treat plan. For each hypothesis, overall alpha will be set at .05, with a Bonferroni correction applied when multiple non-independent tests are conducted. **Missing data** due to dropout or other causes will be addressed with analyses of multiply-imputed datasets generated with SAS PROC MI based on models drawing on all available participant data.

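### Secondary Hypothesis 3 has two conflicting alpha rules (0.05 per test in 5.9, Bonferroni-controlled 0.05 overall in 5.10), and its SBP power labelled as allowing for attrition is the no-attrition figure

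*Combined protocol and SAP*

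**What the plan says.** **Alpha.** For Secondary Hypothesis 3 (combination better than each single treatment on co-morbidity measures), section 5.9 states: "since the outcomes of interests were chosen based on previous studies instead of random selection, alpha for each test is set at 0.05". Section 5.10 names this hypothesis among the analyses it covers and states: "For each hypothesis, overall alpha will be set at .05, with a Bonferroni correction applied when multiple non-independent tests are conducted". It gives no exemption and does not say which outcomes or comparisons form the family.

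Elsewhere 5.9 does correct. For the primary hypothesis, which has the same two-comparison structure: "We set the significance level at 0.025 to adjust for multiple testing". For Secondary Hypothesis 2: "Since there are 3 treatments, multiple-testing Bonferroni-adjusted significance level is set at" 0.05/3.

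**Power.** Section 5.9 bases power on two-sample t-tests of change scores and says that n=30 "per treatment will result in power of ~80% on all the tests except for SBP", citing Table 3. Table 3 prints SBP power of 42.5% (difference 3.8) and 47.3% (difference 4.12). The next sentence reads: "The power is close to 80% for PSQI and hemoglobin a1c, but 42-47% for systolic blood pressure, assuming 10% attrition". The paragraph closes by claiming 80% power for most outcomes.

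**The concern.** The two sections give different significance thresholds for the same tests. The comparisons of the combination with exercise alone and with weight loss alone share the combination arm, and all outcomes come from the same participants. The tests are therefore non-independent, and the condition in 5.10 for a Bonferroni correction is met. An analyst could cite the protocol for 0.05, 0.025 or a smaller level, and the choice could be made after the data are seen.

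The SBP figures are offered first as the n=30 result and then as the result after 10% attrition. They cannot be both.

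**Working it through.** **Inputs (5.9 and Table 3).** SD of change: PSQI 1.8, SBP 10, HbA1c 0.1. Between-arm differences: PSQI 1.15 and 1.26, SBP 3.8 and 4.12, HbA1c 0.07 and 0.077. There are 30 per arm; 10% attrition leaves 27.

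**Formula.** Power = P(T > t_crit), where T is noncentral t with 2n − 2 df and noncentrality (difference/SD) × √(n/2). The test is one-sided.

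**Step 1: reproduce Table 3.** For SBP 3.8 at n=30, noncentrality is 0.38 × √15 = 1.472 and t_crit(58) = 1.672, giving 42.45%. All six cells match at 30 per arm, one-sided 0.05 (first row of the table in step 4). A two-sided 0.05 test at n=30 gives SBP about 30.5% and 34.8%, which does not match. The document text gives no sidedness for Table 3, so one-sidedness is inferred from the six matches.

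**Step 2: what 10% attrition means here.** The primary hypothesis's 82.2% with attrition reproduces at 27 per arm (82.24%; 86.14% at 30). The within-arm SBP figure of 96% also reproduces at 27 (95.94%; 97.36% at 30).

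**Step 3: SBP with attrition.** For SBP 3.8 at n=27, noncentrality is 0.38 × √13.5 = 1.396 and t_crit(52) = 1.675, giving 39.48%. For SBP 4.12 the result is 44.01%. The stated pair is 3.0 and 3.3 points too high.

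**Step 4: effect of the alpha rule (change-score t-test, one-sided).**

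| n/arm | alpha | PSQI (%) | SBP (%) | HbA1c (%) |
|---|---|---|---|---|
| 30 | 0.05 | 78.8 / 85.0 | 42.5 / 47.3 | 85.0 / 90.4 |
| 27 | 0.05 | 74.9 / 81.4 | 39.5 / 44.0 | 81.4 / 87.4 |
| 30 | 0.05/2 | 68.2 / 76.0 | 30.4 / 34.8 | 76.0 / 83.5 |
| 27 | 0.05/2 | 63.5 / 71.4 | 27.8 / 31.8 | 71.4 / 79.3 |
| 27 | 0.05/6 | 45.6 / 54.3 | 15.0 / 17.8 | 54.3 / 64.0 |

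Divisor 2 is the two comparisons; divisor 6 is two comparisons times three outcomes. The protocol names neither, so both are assumptions.

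**Step 5: error rate at 0.05 per test.** Two one-sided comparisons sharing an arm have correlation 0.5, and the joint rejection probability under the null is 0.0122. At least one false positive: 0.10 − 0.0122 = 0.0878. Over three outcomes, assumed independent: 1 − (1 − 0.0878)³ = 0.241. Positive correlation would lower this.

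**Step 6: results that change status.** Critical difference at 27 per arm = t(52) × SD × √(2/27), with t = 1.675 at 0.05 and 2.007 at 0.025:

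- PSQI: 0.82 and 0.98 points
- SBP: 4.56 and 5.46 mmHg
- HbA1c: 0.046 and 0.055 percentage points

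On a one-sided test, an observed difference between the two values is significant under 5.9 but not at divisor 2.

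**Step 7: allowance for ANCOVA.** With equal pre and post variances, baseline adjustment multiplies the change-score variance by (1 + r)/2. The documents give no pre-post correlation r; I assume 0.95 down to 0.5, with df kept at 52. At 27 per arm and 0.025:

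- First scenario: PSQI 64.6–75.8%, SBP 28.4–35.3%, HbA1c 72.5–83.0%
- Second scenario: PSQI 72.5–83.0%, SBP 32.4–40.4%, HbA1c 80.3–89.4%

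At divisor 6 the best cell (HbA1c 0.077) reaches 65.2–78.3%.

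**The case against.** The strongest reply is that 5.9 gives a deliberate, reasoned rule for this hypothesis, and that a specific rule overrides the general sentence in 5.10. That may be the intent, but it does not settle the matter. Section 5.10 is the analysis section and is unqualified. The reason in 5.9 concerns how outcomes were picked and says nothing about the two comparisons per outcome, which the primary hypothesis does correct.

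A second reply is that the divisors are not the protocol's, and that if the claim requires beating both single treatments jointly, no split over the two comparisons is needed and 8.8% is not its error rate. This has some force. However, the primary hypothesis is worded the same way and uses 0.025, and 5.10 should name the family in any case.

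Third, the planned analysis is not the t-test used for power: "we will use an analysis of covariance (ANCOVA) approach to examine treatment effects on post-intervention". Section 5.9 adds: "Having repeated measures for some of these variables will further increase power". Both could raise power. At 0.05 and 27 per arm with an assumed r of 0.7, PSQI is 80.7% and 86.6% and HbA1c 86.6% and 91.7%. So the closing 80% claim is broadly fair for two of the three outcomes if 5.9's alpha is kept, and the power criticism depends on 5.10 governing.

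The ranges in step 6 also assume a one-sided final test, and 5.10 states no sidedness. With a two-sided 0.05 test the PSQI threshold is already 0.98.

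Finally, the SBP error is small and falls on an outcome the protocol already treats as underpowered. That stands: it is a labelling correction.

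**Conclusion.** Both points hold. The alpha conflict is the important one: the protocol gives two rules for the same tests, and the choice changes which co-morbidity results may be called significant. This rests on the text alone.

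The SBP range is mislabelled by about 3 points; that rests on the inferred one-sided 0.05 test and on the protocol's own use of 27 per arm for 10% attrition. Attrition alone leaves the description of PSQI and HbA1c as close to 80% acceptable.

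The larger loss of power is conditional on 5.10 governing, on the divisor, on the number of completers and on r. On the protocol's own change-score basis at 27 per arm, no between-arm scenario reaches 80% at divisor 2 or 6. At 30 per arm and divisor 2, HbA1c at 0.077 does (83.5%), and ANCOVA could lift some PSQI and HbA1c cells above 80%. SBP stays far below 80% in every case examined. The closing 80% claim is supported for the within-arm tests (stated as 99%, 96% and above 99%), but not for the between-arm tests on the protocol's power basis if 5.10 applies.

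**What to change.** 1. Adopt one alpha rule for Secondary Hypothesis 3. Either apply 5.10 and name the family (which outcomes, how many comparisons), or write the 0.05-per-test exception into 5.10 and label those results as not multiplicity-controlled.
2. State whether the power calculation and the final tests are one-sided.
3. Restate Table 3 and the SBP range at 27 per arm at the chosen alpha. If one-sided 0.05 is kept, SBP becomes 39.5% and 44.0%.
4. If 5.10 governs, limit the closing 80% claim to the within-arm tests or replace it with the recomputed between-arm values. If 5.9's alpha is kept, say that the claim covers PSQI and HbA1c only.
5. If credit is taken for baseline adjustment or repeated measures, state the assumed correlation.

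The cost is text and recalculation; the sample size does not rest on Table 3. The drawback is either lower stated between-arm powers or, if the exception is kept, no error control across the Secondary Hypothesis 3 tests.

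### Section 5.10 does not say how unequal AHI variances between arms are handled; if the SDs of 5 and 12.5 in section 5.9 both held, the default pooled error term would roughly halve power for the key contrast and inflate type I error in tests involving exercise alone

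*Combined protocol and SAP*

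**What the plan says.** **Sizing (section 5.9).** The Primary Hypothesis is sized on weight loss alone vs exercise + weight loss, with 30 per arm and a difference of 4 (14.9 vs 10.9) "in AHI reduction between the treatments assuming treatment standard deviations of 5". On alpha the plan says "We set the significance level at 0.025 to adjust for multiple testing", without giving sidedness. Stated power is 86%, or 82.2% with 10% attrition. The plan expects more power for the comparison with exercise alone. For Secondary Hypothesis 2, sized on one-sided paired t-tests at 0.05/3 = 0.017, it says of exercise alone that "we set the mean±SD reduction in AHI (baseline minus post-treatment) at 7.6 ± 12.5 (24% reduction) for the power calculation". The same section reports an SD of change of 13 in the previous exercise trial. It also prints AHI SDs of 5.6 before and 4.4 after exercise, and 5.6 and 5.2 for each of the two weight-loss arms.

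**Analysis (section 5.10).** Post-intervention AHI goes into an ANCOVA "with treatment as the primary independent variable, and adjusting for baseline outcome value" and other covariates. For Secondary Hypothesis 2, the pre-post comparison in each arm is a simple main effect "of time) in the context of a repeated measures ANCOVA". No arm-specific variance, Welch-type test, robust standard error or separate error term is mentioned. The preliminary look at distributions has no decision rule attached. SAS PROC GLM is named only for the mediation models.

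**The concern.** The sizing treats each comparison on its own: a two-arm test for the key contrast, and a paired test within the exercise arm. The analysis section puts all arms into one model. A standard ANCOVA estimates one error variance from all three arms and uses it for every contrast. If exercise alone is much more variable than the two weight-loss arms, that shared estimate is too large for the contrast between those two arms and too small for any test involving exercise alone.

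The Primary Hypothesis claims superiority over both single treatments. Pooling would then make one of its two comparisons heavily conservative and the other anti-conservative. The power and error rates in section 5.9 would not be those of the analysis in section 5.10.

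**Working it through.** **1. Reproduce the plan's figures.**

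- Key contrast, two-sample t-test, noncentrality 4 / (5·√(2/n)). At n=30: 4/1.291 = 3.10 on 58 df, power 86.1%. At n=27: 4/1.361 = 2.94 on 52 df, power 82.2%. Both match the plan at one-sided 0.025, which is the same as two-sided 0.05 here. Two-sided 0.025 gives 78.5% and 73.5%, which do not match.
- Exercise-alone pre-post, paired one-sided t-test at 0.017, noncentrality 7.6 / (12.5/√n). At n=30: 7.6/2.282 = 3.33, power 86.0%. At n=27: 81.6%. The plan states 86.0% and 82%.

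**2. Pool the SDs used in those two calculations** (12.5 for exercise alone, 5 and 5 for the other arms).

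Pooled SD = √((12.5² + 5² + 5²)/3) = √(206.25/3) = 8.29.

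- Key contrast, n=30: the model's standard error is 8.29·√(2/30) = 2.14; the true one is 1.29. With critical t = 1.99 on 87 df, the observed difference must exceed about 4.26, more than the assumed difference of 4.
- Exercise + weight loss vs exercise alone, n=30: model standard error 2.14; true standard error √((12.5² + 5²)/30) = 2.46.
- Exercise-alone pre-post, n=30: model standard error 8.29/√30 = 1.51; true standard error 12.5/√30 = 2.28.

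Simulation (400,000 trials per setting, pooled variance on 3n−3 df) gives:

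| Quantity | Arm-specific variance | Pooled |
|---|---|---|
| Key-contrast power, two-sided 0.05, n=30 / 27 | 86.1% / 82.2% | 43.2% / 37.3% |
| Key-contrast power, two-sided 0.025, n=30 / 27 | 78.5% / 73.5% | 26.8% / 22.1% |
| Type I error, exercise + weight loss vs exercise alone, nominal 5% | about 5% | about 9% |
| Type I error, exercise-alone pre-post, nominal one-sided 1.67% | 1.67% (paired t) | about 8% |

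Change-score SDs stand in here for baseline-adjusted residual SDs.

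**3. How far the result depends on the inputs** (pooled key-contrast power, two-sided 0.05, n=30 / 27).

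- Exercise SD 9, others 5: 68% / 62%. Exercise SD 7: 79% / 74%.
- SDs 12.5/5/5 with baseline adjustment, assuming a baseline-change correlation of 0.3 to 0.5 (the plan gives none): 47–57% / 41–50%. The type I inflation is essentially unchanged.
- All SDs 5: pooling does no harm. All SDs 12.5: pooling does no harm either, but power is only about 23% at n=30.

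**4. Check the printed SDs against each other.** The SD of a difference cannot exceed the sum of the two SDs. For exercise alone that limit is 5.6 + 4.4 = 10.0, so 12.5 cannot hold alongside the printed pre and post SDs.

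**The case against.** The strongest reply is that the plan never states 12.5/5/5 as a joint variance structure. The two SDs come from separate calculations. The expectation of higher power against exercise alone points to a common SD: with SD 5 in both arms, a difference of 14.9 − 7.6 = 7.3 has power above 99%, whereas with SDs of 12.5 and 5 a Welch test has about 82.5% at n=30, below 86.1%. Moreover, the ANCOVA outcome is post-treatment AHI, and the printed post-treatment SDs are 4.4, 5.2 and 5.2. Pooled, these give √((4.4² + 5.2² + 5.2²)/3) = 4.95 and key-contrast power of 86.0% and 82.1%, in line with the plan. On that reading nothing is lost.

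This stands as a limit on size. It does not settle which SDs are right, because the printed values are mutually inconsistent.

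A second reply is that pooling is inferred: it is the default of the named models, not a stated choice, and simple effects of time can be tested with an error term per arm. That is true, and it is why the point is a missing specification. A third is that the planned order-restricted contrasts were not simulated. The figures above concern the ordinary pairwise contrasts on which section 5.9 bases its power.

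A reader might infer that the planned analysis will more than halve the power of the trial. The documents do not support that as fact. It needs both SDs to hold and the pooled default to be used. Even then the loss at n=30 is almost exactly half (86.1% to 43.2%), and baseline adjustment reduces it.

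**Conclusion.** The plan leaves variance handling unspecified in a place where its own inputs make it matter. If the SDs of 5 and 12.5 both held and the default pooled error were used, key-contrast power would be about 43% (n=30) or 37% (n=27) instead of 86% and 82%. Type I error would be about 9% at nominal 5% against exercise alone, and about 8% at nominal one-sided 1.67% for the exercise-alone pre-post test.

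These figures are conditional on a pair of SDs that may be inconsistent planning inputs and not a forecast of unequal variances. Two conclusions do not depend on which SDs are right: section 5.9 needs reconciling, and the variance assumption should be fixed before the data are seen.

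**What to change.** 1. Reconcile the AHI SDs in section 5.9 (5, 12.5, 13, and the printed pre and post SDs), say which are SDs of change and which of level, and restate the power, including whether 0.025 is one- or two-sided.
2. In section 5.10, fit the AHI ANCOVA with a separate residual variance per arm and Satterthwaite or Kenward-Roger degrees of freedom (for example SAS PROC MIXED with residual variance grouped by treatment), or estimate each primary contrast from an ANCOVA on its own two arms. State how the order-restricted contrasts use these variances.
3. Carry this through multiple imputation: fit the same model to each imputed dataset before combining, and let the imputation model allow the variance to differ by arm.
4. Test Secondary Hypothesis 2 with within-arm paired t-tests on AHI change, as section 5.9 already assumes.

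**Cost.** SAP wording and one model option; no extra participants or visits. If the variances are equal, about 0.2 to 0.6 power points are lost. If exercise alone is slightly less variable, the loss is about 3 points: with SDs 4.4/5.2/5.2, the key contrast on its own arms has noncentrality 4/(5.2·√(2/30)) = 2.98 and power 83.4%, against 86.0% pooled at n=30. Part of that pooled advantage comes from a standard error that is slightly too small (based on 4.95 where 5.2 applies).

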Many (n=104) of the candidates were excluded at the stage of screening because they were no longer interested, and a primary disincentive was that they were to avoid trying to lose weight. The potential for weight loss will likely make the proposed study relatively more attractive to candidates. About 200 other candidates were excluded for reporting that they were trying to lose weight. For the present study, we propose a less conservative approach based on this criterion, in which we will exclude only those individuals who have lost $\geq 5\%$ in the previous 6 months weight or who are involved with an experimental weight loss program or another structured weight loss regimen, such as Weight-Watchers (**5.3.3.1**).

4.1.2.2. Retention and Adherence. Of the N=43 participants who were randomized to the treatments, 5 dropped out of the study at an average of 4.6 ± 0.2 weeks into the intervention. Four participants in the exercise training intervention needed to switch from the treadmill to cycle ergometer training due to temporary development of shin splints. Based on this finding, as well as the goals of customizing the exercise to participants' preferences and being more inclusive in participant selection, participants in the proposed study will perform treadmill, cycle ergometer, or elliptical trainer exercise (or some combination). The participants who completed all 12 weeks of the exercise training intervention attended $93.1 \pm 1.7\%$ of the prescribed sessions and completed $88.6 \pm 2.1\%$ and $84.4 \pm 2.9\%$ of the prescribed aerobic and resistance exercise doses, respectively. The participants who completed the 12-week stretching intervention attended $86.9 \pm 2.0\%$ of the prescribed sessions. This high adherence results can be attributed to the screening and personal attention paid to the participants, as proposed here. Participants also adhered to the requests to maintain their usual physical activity and dietary habits, as assessed with an odometer and questionnaire, respectively.

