5.13. Potential Problems and Limitations of Methods. Excellent participant recruitment will be paramount. We previously assessed N=43 OSA subjects over 2 yr for consultant [name]’s dissertation. However, for the proposed study, we have a much closer association with Sleep Medicine at the VA. The director, co-investigator [name], interprets about 25 new cases of OSA per week. She and the staff can inform these patients about the study. We would need to recruit only 2% of these cases if this was our only source of subjects. We will also seek a HIPAA waiver to provide information about our study to the 30,000 Phoenix VA patients who have been diagnosed with OSA. Other factors that will benefit recruitment include an expanded subject age range (from 18-55 to 18-60 years of age); less stringent inclusion criteria; and having [name] as a consultant. If we still are unable to recruit enough veterans, we will request permission to include non-veterans.

Retention of participants will be critical for the success of the study, and sedentary and/or overweight individuals are high risk of drop-out or poor adherence to exercise. However, a run-in period will reduce the number of non-adherents, and personalized attention throughout the intervention should promote retention. For our previous study, only 5 of the 43 participants who began the intervention discontinued the study. Another benefit for retention is that the entire study will be conducted at the Phoenix VA, whereas in our previous proposal, the PSG, interventions, and laboratory measures were going to be conducted off-site at USC.

The intervention will be more conducive to exercise and weight loss than is typical, which will limit the study’s generalizability. Presently, we believe it is most imperative to establish efficacy. As exemplified by the VA “Move!” program, there is an accelerated focus on exercise and weight loss which could facilitate these behaviors among veterans with OSA at no cost. Subsequent studies could compare lab vs. home intervention.

Follow-up assessments will be influenced by uncontrolled factors, e.g., the extent to which participants maintain or initiate exercise, weight loss, or PAP. Ethics dictate allowing post-study treatments. Careful assessment of these should permit some conclusions regarding the chronicity of post-treatment improvements.

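### The main ANCOVA adjusts for percentage of sessions attended, a post-randomisation variable, so its treatment coefficient is not the effect of assignment that the intent-to-treat plan calls for

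*Combined protocol and SAP*

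**What the plan says.** Section 5.10 (Statistical Analysis) uses a single ANCOVA for the Primary Hypothesis (AHI at post-test), Secondary Hypothesis 1 (AHI at 3-month follow-up) and Secondary Hypothesis 3 (comorbidity measures). Treatment is the main independent variable. The model is described as "adjusting for baseline outcome value, intervention dose (percentage of sessions attended), baseline outcome value, age, sex", then duration of OSA diagnosis and any other covariates judged relevant.

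The adjusted means feed the confirmatory step, described as "order-restricted comparisons (isotonic contrasts) of covariate-adjusted means to test for the predicted ordered patterning of the three treatment means". Before that step the section has a simpler one: "We will test for ordering of treatment means (not adjusted for covariates", run as an order-restricted test in R. The section also states: "Analyses will be based on an intent-to-treat plan".

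Secondary Hypothesis 2 has its own repeated measures model, and the attendance term is not listed for it. Nothing in the document labels the attendance adjustment as a sensitivity, per-protocol or dose-response analysis.

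**The concern.** Section 5.5 places randomisation after baseline, so attendance can only arise after assignment. Two features make it unsafe as a covariate.

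- **It can depend on the arm.** Planned sessions are 4 × 16 = 64 for Exercise Alone (5.5.1), 16 for Weight Loss Alone (5.5.2) and 64 + 16 = 80 for the combined arm (5.5.3). One missed session costs 1/64 = 1.6, 1/16 = 6.25 or 1/80 = 1.25 percentage points. Equal percentages are therefore not equal doses, and the burden differs between arms.
- **It can share causes with the outcome.** People who attend more may differ in motivation or health. Section 5.6.4 also removes participants at Weeks 5 and 10 for health deterioration or for impaired values that include blood pressure and hemoglobin A1c. If later sessions then count as missed, early outcome values partly determine attendance.

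The primary question is whether assignment to exercise plus weight loss lowers AHI more than assignment to either treatment alone. If mean attendance differs between arms and is related to AHI change within arms, the adjusted contrast moves away from that effect. The result could be a false claim of additive benefit or a real benefit hidden.

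**Working it through.** **1. The plan's own power (5.9).** Inputs: difference in AHI reduction 14.9 − 10.9 = 4, SD 5, 30 per arm, or 27 after 10% attrition. The level is given by "We set the significance level at 0.025 to adjust for multiple testing"; sidedness is not stated. Two-sample noncentral t power:

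| Test | n = 30 | n = 27 |
|---|---|---|
| One-sided 0.025 | 86.1% | 82.2% |
| Two-sided 0.025 | 78.5% | 73.5% |

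The first row matches the stated 86% and 82.2%. One-sided 0.025 is therefore inferred, and both versions are shown below. Neither calculation contains an attendance term.

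**2. Bias formula.** Let D be the effect of assignment on AHI reduction (combined minus comparator), b the within-arm AHI reduction per attendance point, and g the gap in mean attendance (combined minus comparator). In a linear model without interaction:

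adjusted coefficient = D − b × g

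The bias is −b × g. It is zero when g = 0 or b = 0, and it changes sign with either.

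**3. Inputs for an illustration.** The only attendance figures in the document come from the previous 12-week trial (4.1.2.2), among completers, in a different comparison: "exercise training intervention attended $93.1 \pm 1.7\%$ of the prescribed sessions" against "stretching intervention attended $86.9 \pm 2.0\%$ of the prescribed sessions". That gives |g| = 93.1 − 86.9 = 6.2 points. Assumed, with no source in the document: attendance SD 10 points and b = 0.1 or 0.2. The second slope is a direct 0.1 plus a shared trait worth 2 events/h per SD, correlated 0.5 with attendance: 0.1 + 2 × 0.5/10 = 0.2.

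**4. Shift in the primary contrast, D = 4.**

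- Combined arm attends less: 4 + 0.1 × 6.2 = 4.62; 4 + 0.2 × 6.2 = 5.24.
- Combined arm attends more: 4 − 0.62 = 3.38; 4 − 1.24 = 2.76.
- As a share of 4: 0.62/4 = 16% and 1.24/4 = 31%.

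**5. Error rates and power.** Simulation of two arms, 27 per arm, SD 5, 200,000 trials per scenario. Each cell gives the results for b = 0.1 and b = 0.2.

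| Scenario, attendance in the model | One-sided 0.025 | Two-sided 0.025 |
|---|---|---|
| Type I error, D = 0, g = −6.2 | 6.4% / 15.0% | 3.9% / 9.3% |
| Power, D = 4, g = +6.2 | 65% / 54% | 54% / 42% |
| Power, D = 4, g = 0 | 83% / 88% | 74% / 80% |

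Without the term, the estimate is 4.00, power is 82.2% or 73.5%, and type I error is 2.5%.

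**6. Closer to the planned model.** A three-arm ANCOVA on post-treatment AHI adjusted for baseline (32.2, SD 5.6; 100,000 trials) gives nearly the same for combined against weight loss: 4.62 / 5.24 or 3.39 / 2.76. Power when the combined arm attends more is 67% / 55% one-sided and 56% / 44% two-sided. For combined against exercise alone (14.9 − 7.6 = 7.3), the estimate becomes 7.92 / 8.54 or 6.68 / 6.06. Power stays at 99% or more, but only at SD 5.

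**7. Dependence on SD.** Section 5.9 reports an SD of change of 13 in the previous trial, and 12.5 is used for exercise alone under Secondary Hypothesis 2. With SD 12.5 in step 5, type I error falls to 3.8% / 5.3% one-sided and 2.8% / 3.3% two-sided. The shift in the estimate stays at 0.6 to 1.2, because the formula does not contain the SD. Power without the attendance term for combined against exercise alone (difference 7.3, 27 per arm) is then 56% one-sided or 44% two-sided if both arms have SD 12.5. If only the exercise arm does, it is about 78% or 68%.

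**The case against.** - **Intent-to-treat may describe only the analysis set.** The sentence sits close to the one on missing data and can be read as meaning that everyone is analysed as randomised. That reading is possible, but keeping everyone in the analysis does not restore the effect of assignment once the model conditions on attendance.
- **Efficacy is the stated priority.** Section 5.13 says "Presently, we believe it is most imperative to establish efficacy", which may explain the term. Conditioning on observed attendance still does not give a randomised efficacy comparison, because those who attend differ from those who do not.
- **An unadjusted comparison exists.** The ordering test of raw means is free of the problem. It does not replace the baseline-adjusted contrasts of the combined arm with each single treatment.
- **The size is unknown and may be nil.** This stands. All three arms are active, attendance is a percentage of each arm's own schedule, and the 6.2 points come from another comparison. The run-in, make-up, telephone and unsupervised sessions may narrow a gap, though they do not guarantee equality.
- **The error rates are fragile.** This also stands. They use SD 5 and shrink at SD 12.5. They come from t or ANCOVA tests, without the isotonic contrast, age, sex or multiple imputation. Where the slope is purely causal, a zero effect of assignment implies a direct benefit at equal attendance that lower attendance cancels. The 6.4% is then an error only against the null hypothesis about assignment; the 15% scenario adds confounding.

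**Conclusion.** The concern holds. As written, the ANCOVA for the Primary Hypothesis and Secondary Hypotheses 1 and 3 does not estimate the effect of assignment, and this conflicts with the intent-to-treat statement in the same section. The conclusion rests on the model specification and on attendance arising after randomisation, and does not depend on the simulations.

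The documents fix neither the size nor the direction of the bias. If better attendance goes with greater AHI reduction, the combined arm's advantage is overstated when that arm attends less and understated when it attends more; if the slope has the opposite sign, the directions reverse. The illustrative shift of 0.6 to 1.2 AHI units against a planned difference of 4 assumes a slope of 0.1 to 0.2 per point, a gap of 6.2 points and a linear model. The error and power figures also assume SD 5. The defect affects the primary analysis and should be corrected before any outcome data are analysed.

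**What to change.** Delete the attendance term from this ANCOVA, and hence from the covariate-adjusted isotonic contrasts. Keep the other planned covariates, limited to pre-randomisation values. Suggested wording:

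> The model adjusts for the baseline value of the outcome, age, sex and time since OSA diagnosis; for inflammation outcomes, also for the confounders named in 5.6.2; and for any further relevant covariates. All covariates are taken as recorded before randomisation.

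Report attendance by arm descriptively, with exercise and counselling sessions shown separately; section 5.11 already plans to assess adherence. Present any dose-response analysis as exploratory and label it so. Attendance may remain in the multiple imputation model, where it can help to predict missing outcomes.

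The cost is a change of wording only. The stated 86% and 82.2% were computed without an attendance term and stand as they are. The one thing given up is some precision if attendance turns out equal across arms: under the assumptions above, the term would have raised power from 82% to 83–88% (one-sided 0.025) or from 73.5% to 74–80% (two-sided 0.025).
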